Clinical trials evaluating EGFR-TKIs with PARPi failed to achieve their primary endpoint of PFS, possibly due to a lack of patient selection based on HRD score or other molecular criteria [22]. However, subsequent analyses of the GOAL trial found a stronger synergy between gefitinib (a 1st generation TKI) and olaparib in tumours with higher

BRCA1 expression [23], supporting a predictive role for targeting DNA damage repair pathways. In operable NSCLCs, the percentage of HRD positive tumours is ~20-30% [24], suggesting that the acquisition of HRD status could be an early event. Importantly, a similar incidence was observed in a Chinese cohort of any-stage EGFRm or ALK-rearranged NSCLC patients in which the cases with high HRD score are ~33% of the total [18]. The sensitivity of EGFRm tumours to platinum-based doublets [25], which is a known characteristic of HRD-positive tumours, and a larger compendium evidence of chromosomal instability further support exploring the role of HRD in EGFR-mutated lung cancer, paving the way for new targeted therapeutic approaches [26].

The HER Project

With the HER project, we will investigate the role of HRD and genomic instability (GSS) in EGFRm NSCLC by i) defining the fraction of metastatic EGFRm tumours with HRD positive score, ii) correlating HRD score with patient outcomes, and iii) assessing the synergic efficacy of EGFR-TKIs plus PARPi based on the HRD score in different preclinical settings, ranging from cell lines to a murine model of spontaneous EGFRm lung cancer. We expect that this drug combination will be effective in a specific subset of EGFR tumors. However, even if we won't observe any relevant findings by targeting this pathway, our work will increase our knowledge about DNA damage repair and drug resistance in EGFRm tumours.

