5. OBJECTIVES AND ENDPOINTS

Objectives	Endpoints	Time point(s)
Primary Objective To evaluate prevalence of HRD in our internal cohort of metastatic EGFRm NSCLC	Primary Endpoint Proportion of EGFRm NSCLC with an HRD positive score evaluated by AmoyDx HRD Panel or similar (GSS \geq 50).	At T0 on baseline tumour samples
Secondary Objectives To assess correlations between HRD score (pos/neg) and: 
 - Clinical variables (PFS, OS, metastatic sites) - Molecular events (type of EGFR mutations, VAF, drug resistance mechanisms i.e. gene amplification) 	Secondary Endpoints Overall survival (OS), Progression-free survival (PFS), tumour genomic mutations.	At T0 on baseline tumour samples
Exploratory Objectives 
 - To assess the efficacy of osimertinib and olaparib combination in TKI-naïve EGFRm NSCLC cell lines (HCC-4006, HCC-827, and HCC-2935, ranging from low to high HRD score); - To test the drug combination in patient-derived models of EGFRm tumours (PBMCs, organoids, and PDXs); 	Tumor growth, cellular viability, drug toxicity.	N/A

- To rule out toxicity the drug combination and assess treatment response, thanks to our immune competent GEMM model of EGFRm16 and TP53 wt/null.

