14. STATISTICS

14.1. Description of Statistical Methods

The statistical analysis will address the primary, secondary, and exploratory objectives of the study. For descriptive statistics, continuous variables will be summarized using mean, median, range, and standard deviation, while categorical variables will be described using frequency and percentage. Comparisons between groups (e.g., HRD positive vs HRD negative) and time-to-event analyses will be performed with appropriate statistical tests, as detailed in Section 14.4. Statistical significance will be set at a two-sided p-value < 0.05. Analyses will be performed through statistical software such as Microsoft Excel, R, and SPSS.

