14.2. Sample Size Determination

According to the literature, the expected prevalence of HRD positivity in NSCLC ranges from 20–30% in early-stage tumours [24]. A similar incidence was observed in a Chinese cohort of any-stage EGFRm or ALK-rearranged NSCLC patients in which the cases with high HRD score are ~33% of the total [18].

Therefore, to obtain an adequate number of patients to allow subgroup analyses and explore clinical and molecular correlations, we calculated a sample size of 100 patients (50 retrospective; 50 prospective) to conduct an exploratory proof-of-concept study, in which we expect to observe around 25 HRD-positive cases (the precision of the estimate corresponds to a 95% confidence interval with a half-width of approximately 8.5 percentage points, which is considered clinically relevant). Based on the historical caseload at IRCCS Ospedale San Raffaele (\approx 15 eligible patients/year), recruiting the planned sample over 4 years is feasible. For the retrospective cohort, we estimate that \approx 30% of patients have insufficient residual archival tumor tissue, therefore the planned 50 patients will be included considering a longer interval (1/1/2020 - 30/09/2025).

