14.4 Statistical Design

For the Primary and Secondary Objectives, continuous variables will be summarized using mean, median, range, and standard deviation. Categorical variables will be described using frequency and percentage. To test association between categorical variables, chi-squared test will be applied. To compare survivals between groups (i.e. HRD positive vs negative, cut-offs to be explored) log-rank test will be applied. Time-to-event outcomes will be represented using Kaplan-Meier curves.

For the Exploratory Objectives, parametric and non-parametric analyses will be used to compare differences in cell lines and phenotypes between groups. For the *in vivo* studies, differences in tumour size and phenotype will be evaluated at different timepoints and compared with t-test. For all statistical tests, $p < 0.05$ will be considered statistically significant.

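### In vivo tumour size is compared by t-test with no mention of size at treatment start, which can cost power in this exploratory analysis

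*Protocol*

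**What the plan says.** Protocol section 14.4, repeated in the synopsis under Statistical Design, gives one method for the animal experiments: "differences in tumour size and phenotype will be evaluated at different timepoints and compared with t-test". The sentence before it is wider, since "parametric and non-parametric analyses will be used to compare differences in cell lines and phenotypes between groups", but the in vivo sentence names only the t-test. It mentions no measurement at treatment start, no log scale and no model over time.

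The exploratory endpoints in section 5 are "Tumor growth, cellular viability, drug toxicity". The animal work includes a "murine model of spontaneous EGFRm lung cancer" (section 4) and, among the patient-derived models, PDXs (section 5), which section 3.2 defines as patient tumour implanted into mice.

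Section 14.1 states that "Statistical significance will be set at a two-sided p-value < 0.05". The protocol gives no number of animals, effect size, tumour-size spread, start-to-end correlation or power for the in vivo comparisons.

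**The concern.** The endpoint is growth, but the quantity put into the test is size. Where tumours arise spontaneously, animals can be expected to enter treatment with different burdens. Size at a later timepoint then carries that starting variation as well as growth under treatment. Starting variation that the analysis leaves in the error term makes the comparison less sensitive, and this matters most in small groups. A real effect of the combination could be missed when the same animals, analysed with their starting size, would have shown it.

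Tumour sizes may also be right-skewed, which would cost a raw-scale t-test some further power. The protocol does not describe the distribution, so this is an assumption.

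**Working it through.** **The plan's own figure.** The only design figure in the protocol concerns patients: a "95% confidence interval with a half-width of approximately 8.5 percentage points". With 25 positives in 100, 1.96 × √(0.25 × 0.75 / 100) = 0.0849, or 8.5 points. It reproduces, but it has no bearing on the animal experiments, for which there is no figure to check.

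**Inputs.** From the protocol: a t-test on tumour size and two-sided alpha 0.05. Assumed: two equal groups of 8, log-normal sizes, and a true halving of size (a log difference of ln 2 = 0.693). The SD of final log size (σ) and the start-to-end correlation (ρ) are varied.

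**Model.** Log end size = log start size + growth + treatment effect. The SD of log start size is ρσ and the SD of log growth is σ√(1 − ρ²). At σ = 0.7 and ρ = 0.7 these are 0.49 and 0.50.

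**Hand check at σ = 0.7, ρ = 0.7, 8 per group.** The noncentrality is (0.693 / SD) × √(8/2), and the critical t on 14 df is 2.145.
- t-test on log end size: SD 0.70, noncentrality 0.693/0.70 × 2 = 1.98, power 45%.
- t-test on log change from start: SD 0.50, noncentrality 0.693/0.50 × 2 = 2.77, power 73%.
- ANCOVA of log end size on log start size uses the same residual SD of 0.50. It spends one degree of freedom on the slope and a little precision on chance imbalance, so its power should fall slightly below 73%.

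**Simulation, 20,000 runs per row, 8 per group, size halved.**

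| σ | ρ | raw-size t-test | log-size t-test | log ANCOVA | raw ÷ ANCOVA |
|---|---|---|---|---|---|
| 0.4 | 0.3 | 87% | 89% | 90% | 0.97 |
| 0.4 | 0.8 | 86% | 90% | 99.8% | 0.86 |
| 0.7 | 0.3 | 36% | 46% | 46% | 0.78 |
| 0.7 | 0.5 | 36% | 45% | 54% | 0.67 |
| 0.7 | 0.7 | 36% | 46% | 70% | 0.51 |
| 0.7 | 0.8 | 35% | 45% | 83% | 0.42 |
| 1.0 | 0.5 | 15% | 25% | 30% | 0.51 |

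Effect size matters too. With final size at 0.35 of control and σ = 0.4, the ratio is 0.99 to 1.00 at every correlation tried. With final size at 0.65 of control, σ = 0.4 and ρ = 0.8, power is 48% against 89%.

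**Where the loss comes from.** At σ = 0.7, ρ = 0.7, moving from raw to log size gains 46 − 36 = 10 points, and adding starting size gains a further 70 − 46 = 24. For a halved size, the raw scale costs about 3 points at σ = 0.4 and about 10 at σ = 0.7 or 1.0. When the correlation is low, starting size adds little, and what loss remains is mainly the scale.

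**False positives.** With no treatment effect, the raw-size t-test rejects in 3.2% to 3.6% of runs at σ about 0.94 (6 to 10 per group) and in about 4% at σ = 0.7 (8 per group). ANCOVA stays near 5%. The issue is power only.

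**The case against.** The strongest reply is that the protocol does not exclude starting size. A t-test on change or fold change from the first measurement would fit its wording. At σ = 0.7, ρ = 0.7 that test reaches 67% on fold change or 73% on log change, against 70% for ANCOVA. So the t-test as such is not the defect, and choice of scale or covariate is often left to a statistical analysis plan. The first part stands: the weakness lies in the quantity named, and a t-test on log change would serve. The second stands only in part, because the protocol does not leave the matter open. It names tumour size as the quantity and the t-test as the method.

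Three stronger readings are tempting and are not supported.
- A reader might infer that the planned test halves the power. That occurs in some assumed settings and not in others, and the protocol supplies none of the inputs.
- A reader might infer that comparing size does not estimate the effect on growth. If the groups start equal on average, the expected difference in log size equals the expected difference in log growth. Only precision differs, and the protocol describes no systematic imbalance.
- A reader might infer more spurious effects. The null error rate does not exceed about 5%.

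It is also fair to say that the spontaneous-tumour argument does not carry over automatically to PDXs, that a log scale fails for tumours that disappear, and that this is an exploratory objective in a study that section 14.5 calls primarily descriptive. The fix allows for the first two, and the last sets the weight of the point.

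**Conclusion.** The point holds as a modest one. Section 14.4 and the synopsis name tumour size and a t-test, with no mention of size at treatment start, for an endpoint of growth in a model where starting burden can be expected to vary. Applied as worded to size at a later timepoint, the test gives away power without raising the false-positive rate.

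Under the assumptions of 8 animals per group, size halved, log-SD 0.7 and correlation 0.7, power is about 35% against 70%. For a halved size the gap shrinks to about 10 points at log-SD 0.7 with correlation 0.3, and to about 3 points at log-SD 0.4 with correlation 0.3. In the central case most of the loss comes from leaving out starting size. The calculation assumes log-normal sizes and starting differences that carry through in full to the end (slope 1 on the log scale). The second assumption favours the log-change t-test. ANCOVA estimates the slope and so does not depend on it.

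The HRD prevalence estimate and the patient survival analyses are unaffected.

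**What to change.** In section 14.4 and the synopsis, replace the t-test for in vivo tumour size with a linear model (ANCOVA) of log tumour size at one named timepoint, comparing groups with adjustment for log tumour size at treatment start. State what is done when a tumour becomes unmeasurable: either a fixed small offset before taking logs, or a rank-based analysis. A t-test on log change from treatment start is an acceptable simpler alternative. Apply this to the spontaneous-tumour model, and to PDXs where a size at treatment start is recorded.

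The cost is a sentence or two of text and one routine regression. The protocol mentions several timepoints but does not say that the first is at treatment start. If it is not, one size measurement per animal at that point is needed. No extra animals are required.

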14.5 Potential biases and mitigation strategies

The study is a pilot investigation with a primarily descriptive intent and will include all advanced lung cancer patients with an EGFR mutation treated with TKI inhibitors as standard of care. Retrospective cohort will include patients in the interval indicated (1/1/2020 - 30/09/2025) and those who have received at least one dose of treatment and for whom survival can be estimated (i.e., at least a date of death available). Only patients for whom insufficient archival tumor tissue is available will be excluded, which should not introduce a selection bias. To limit as much as possible bias related to sample size, a prospective cohort has been planned, in order to broaden the study while maintaining its exploratory nature.

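### In vivo tumour size is t-tested at several timepoints, each at p < 0.05, with no primary timepoint or summary measure, so the chance of a false-positive timepoint exceeds 5%

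*Protocol*

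**What the plan says.** Section 14.4 of the protocol, repeated in the Statistical Design row of the synopsis, covers the Exploratory Objectives. For the in vivo studies it says that "differences in tumour size and phenotype will be evaluated at different timepoints and compared with t-test". The next sentence reads "For all statistical tests, $p < 0.05$ will be considered statistically significant", and section 14.1 makes the threshold two-sided: "Statistical significance will be set at a two-sided p-value < 0.05".

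Section 5 lists the exploratory endpoints as "Tumor growth, cellular viability, drug toxicity". One of the exploratory objectives there, for the genetically engineered mouse model, is "To rule out toxicity the drug combination and assess treatment response".

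The protocol does not name a primary timepoint, a summary measure over time, a longitudinal model or a multiplicity adjustment for this comparison. It also gives no number of timepoints, animals or treatment groups. Section 14.5 describes the whole study in these terms: "The study is a pilot investigation with a primarily descriptive intent".

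**The concern.** The protocol fixes both the test and the rule for calling a result significant. Each additional timepoint is another opportunity to cross 0.05, and nothing says in advance which timepoint counts. If the combination does nothing, an experiment with several timepoints will show at least one significant difference more often than the nominal 5%. Phenotype comparisons and further group contrasts would add more opportunities, in numbers that are not stated.

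There is also a mismatch with the endpoint. Tumour growth is a course over time, and a set of separate cross-sectional tests does not yield a single answer about it.

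At stake is how an exploratory animal result is reported. One favourable timepoint could be presented as a significant treatment effect under the protocol's own rule, at an error rate that the reader would take to be 5%.

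**Working it through.** **The plan's own figure.** There is none to reproduce. The protocol gives no error rate, power or animal number for the in vivo comparison.

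**Inputs from the protocol.** Two-sided 0.05 for every test (sections 14.1 and 14.4); t-test (section 14.4); more than one timepoint, known only from the words "evaluated at different timepoints".

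**Inputs that are assumptions.** Number of timepoints k; 8 animals per arm; two arms; correlation between timepoints of 0.5 to 0.9. None of these is in the protocol.

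**Step 1: independent timepoints**, for example separate animals examined at each time. The chance of at least one p < 0.05 with no true effect is 1 − 0.95^k:

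- k = 2: 1 − 0.9025 = 0.0975
- k = 3: 1 − 0.8574 = 0.1426
- k = 5: 1 − 0.7738 = 0.2262
- k = 8: 1 − 0.6634 = 0.3366

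**Step 2: correlated timepoints**, for example the same animals measured serially. Normal data were simulated with no treatment effect and 8 animals per arm. A two-sample t-test was done at each timepoint, with 40,000 runs per setting (simulation standard error at most about 0.0025). The table gives the proportion of runs with at least one p < 0.05. Correlation is either equal between all timepoints (exchangeable) or decays with distance in time (AR(1)).

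| Correlation | k = 2 | k = 3 | k = 5 | k = 8 |
|---|---|---|---|---|
| Exchangeable 0.5 | 0.092 | 0.126 | 0.188 | 0.260 |
| Exchangeable 0.8 | 0.081 | 0.102 | 0.132 | 0.165 |
| Exchangeable 0.9 | 0.071 | 0.086 | 0.105 | 0.127 |
| AR(1) 0.5 | 0.090 | 0.133 | 0.207 | 0.303 |
| AR(1) 0.8 | 0.080 | 0.107 | 0.155 | 0.224 |
| AR(1) 0.9 | 0.071 | 0.091 | 0.121 | 0.168 |

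The ranges are about 7–9% at 2 timepoints, 9–13% at 3, 10–21% at 5 and 13–30% at 8. Runs with 6 or 10 animals per arm give nearly the same values (at 5 timepoints, 0.104 to 0.202 over the same correlations), so the assumed group size matters little.

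**Step 3: each test on its own.** In the same runs the rejection rate averaged over timepoints was 0.049 to 0.051 in every setting. A single t-test at a single timepoint is therefore valid. The excess comes only from having several of them.

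**Step 4: as multiples of 5%.** Two timepoints at correlation 0.8 to 0.9 give 0.071/0.05 = 1.4 to 0.081/0.05 = 1.6 times. The largest value, 0.303/0.05 = 6.1 times, occurs in one cell only: 8 timepoints with AR(1) 0.5. There the first and last measurements correlate at 0.5^7 = 0.008, which is hard to believe for tumour size in the same animal.

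**The case against.** The strongest reply is that the work is exploratory and preclinical within a study described as a pilot with mainly descriptive aims. The protocol has no rule that one significant timepoint establishes efficacy, so an error rate over all timepoints answers a decision that the protocol does not take. Naming a primary timepoint for an animal experiment could also be left to a later analysis plan.

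Part of this stands. It limits the point to a minor one, and the error rates hold only on the condition that any timepoint may be reported as an effect. It does not remove the point. A descriptive aim would call for estimates with intervals, whereas section 14.4 prescribes tests and a significance threshold for all of them. That is a stated method, and an analysis plan that followed it would inherit the problem.

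A reader might also infer stronger things that the protocol does not support:

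- **That the false-positive rate rises by a fixed multiple, such as two- to sixfold.** The number of timepoints and their correlation are not given, so no single multiplier follows.
- **That ignoring within-animal correlation is itself an error.** Each single between-group test uses one value per animal and holds 5%. Positive correlation lowers the overall rate compared with independent timepoints.
- **That the same animals are measured repeatedly.** Section 14.4 does not say whether measurement is serial or uses separate animals at each time.
- **That late timepoints are biased because animals with large tumours leave early.** The protocol describes no removal of animals.
- **That the mouse data are the only evidence on the combination.** Section 5 also lists cell lines and other patient-derived models.

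**Conclusion.** The point holds in a limited, conditional form. The protocol prescribes several unadjusted t-tests over time at p < 0.05 and does not say which one counts. If any of them can be reported as a significant effect, the false-positive rate exceeds 5% for every number of timepoints from two upwards. The direction is certain under that condition, short of timepoints that are perfectly correlated. The size is not: it rests on assumed timepoints and correlations and ranges from about 7% to about 30% over the settings shown.

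The consequence is confined to the exploratory animal experiments. The estimate of HRD prevalence and the analyses of PFS, OS and molecular features are untouched. This is a minor improvement that is worth making because it is nearly free.

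**What to change.** In section 14.4 and the matching synopsis row, replace the per-timepoint tests, where the same animals are measured serially, by one test per experiment. Either of these will do:

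- a linear mixed model on log tumour volume with treatment, time, their interaction and a random animal effect, tested by one pre-specified treatment contrast; or
- one t-test on a pre-named summary per animal: growth rate, area under the curve or one named day.

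If separate animals are examined at each time, the named-day option still applies. State which design is used. Report differences at the individual timepoints as estimates with confidence intervals, without a significance claim.

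A Bonferroni correction over timepoints would also control the error, but it wastes power when measurements are correlated: in simulations with 6 or 10 animals per arm, 2 to 10 timepoints and correlations of 0.5 to 0.95, the overall rate fell to between 0.014 and 0.048.

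The cost is a short change of wording in two places and slightly more analysis work, with the same animals and data. What is given up is the ability to call a single timepoint significant.

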14.5 Potential biases and mitigation strategies

The study is a pilot investigation with a primarily descriptive intent and will include all advanced lung cancer patients with an EGFR mutation treated with TKI inhibitors as standard of care. Retrospective cohort will include patients in the interval indicated (1/1/2020 - 30/09/2025) and those who have received at least one dose of treatment and for whom survival can be estimated (i.e., at least a date of death available). Only patients for whom insufficient archival tumor tissue is available will be excluded, which should not introduce a selection bias. To limit as much as possible bias related to sample size, a prospective cohort has been planned, in order to broaden the study while maintaining its exploratory nature.

15. ETHICAL AND REGULATORY CONSIDERATIONS

This clinical study will be conducted in accordance with the principles laid down by the 18th World Medical Assembly (Helsinki, 1964) and all applicable amendments established by the World Medical Assemblies, and the ICH guidelines for Good Clinical Practice.

This clinical study will be conducted in compliance with all international laws and regulations; national laws and regulations of the country in which the clinical study is performed; as well as any other applicable guidelines.

